## 2. Target Population

### a. For inclusion into open-label treatment period of Stratum A

Subjects with T2DM with inadequate glycaemic control, defined as central laboratory HbA1c  $\geq 8.0\%$  and  $\leq 11.5\%$  obtained at the screening visit (i.e., Week -18), on stable metformin therapy alone at a dose  $\geq 1500$  mg per day or a maximal tolerated dose for at least 8 weeks prior to screening visit

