### b. For inclusion into open-label treatment period of Stratum B

Subjects with T2DM with inadequate glycaemic control, defined as central laboratory HbA1c  $\geq 7.5\%$  and  $\leq 10.5\%$  obtained at the screening visit (i.e., Week -10), on stable metformin therapy at a dose  $\geq 1500$  mg per day or a maximal tolerated dose AND a DPP-4 inhibitor (free form combination) at the maximum approved dose for at least 8 weeks prior to screening visit

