### c. For inclusion into double-blind treatment period of both Stratum A and B

Subjects with T2DM with inadequate glycaemic control, defined as central laboratory HbA1c  $\geq 7.0$  and  $\leq 10.5\%$  obtained at the Week -2 visit of the open-label treatment period

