## **2.2 Violations and deviations**

Important protocol deviations (IPD) are a subset of protocol deviations that may significantly impact the completeness, accuracy, and/or reliability of the study data or that may significantly affect a subject's rights, safety, or wellbeing.

A list of important protocol deviations and any action to be taken regarding the exclusion of subjects or affected data from the primary efficacy analysis are defined in appendix 1. This list will be finalised before the data has been unblinded. A report will be generated based on both IMPACT and programmatic checking results. IPDs that are determined to have the potential to affect the primary efficacy results are deemed PP Relevant IPDs. Subjects who have any PP relevant IPDs as detailed in appendix 1 will be excluded from the PP analysis set.

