## 8. APPENDIX

### 8.1 Appendix 1 – IPD MASTER LIST

IPD code	IPD Category	Explanation	PP Relevant IPD	Exclusion level
1. Inclusion Criteria Deviations: for subject who did not meet any of below criteria (refer to CSP section 3.1)				
1.1	Did not fulfil eligibility criteria	Subjects must be willing and able to give signed and dated written informed consent		
1.2	Did not fulfil eligibility criteria	
a. For inclusion into open-label treatment period of Stratum A Subjects with T2DM with inadequate glycaemic control, defined as central laboratory HbA1c <math>\geq 8.0\%</math> and <math>\leq 11.5\%</math> obtained at the screening visit (i.e.. Week -18), on stable metformin therapy alone at a dose <math>\geq 1500\text{mg}</math> per day or a maximal tolerated dose for at least 8 weeks prior to screening visit
 
b. For inclusion into open-label treatment period of Stratum B Subjects with T2DM with inadequate glycaemic control, defined as central laboratory HbA1c <math>\geq 7.0</math> and <math>\leq 10.5\%</math> obtained at the screening visit (i.e.. Week -10), on stable metformin therapy at a dose <math>\geq 1500\text{mg}</math> per day or a maximal tolerated dose AND a DPP-4 inhibitor (free form combination) at the maximum approved dose for at least 8 weeks prior to screening visit
 
c. For inclusion into double-blind treatment period of both Stratum A and B Subjects with T2DM with inadequate glycaemic control defined as central laboratory HbA1c <math>\geq 7.0</math> and <math>\leq 10.5\%</math> obtained at the Week -2 visit of the open-label treatment period
 
d. Body mass index (BMI) <math>\leq 40.0\text{kg/m}^2</math> at the screening visit.
	
1. Randomised subjects without Type II diabetes or with central laboratory HbA1c at screening and/or -2 week outside of specified limits such as more than 0.2% outside of specified limits (i.e. violation of inclusion criterion # 2c or screening HbA1c value out of range specified in 2a or 2b)
 
2. Randomised subjects who do not receive stable dose of metformin as of the start of open-label (i.e. Violation of inclusion criterion 2a and 2b)
	Completely Exclude from PP analysis set

IPD code	IPD Category	Explanation	PP Relevant IPD	Exclusion level

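### SAP Appendix 1 item 1.2b sets the Stratum B screening HbA1c floor at 7.0%, where protocol criterion 2b sets it at 7.5%

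*SAP*

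**What the plan says.** Protocol Section 3.1, criterion 2b, admits Stratum B subjects to the open-label period with "central laboratory HbA1c $\geq 7.5\%$ and $\leq 10.5\%$ obtained at the screening visit (i.e., Week -10". Criterion 2c, which governs randomisation in both strata, asks for "central laboratory HbA1c $\geq 7.0$ and $\leq 10.5\%$ obtained at the Week -2 visit".

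SAP Appendix 1 restates these criteria as item 1.2. The header of that group describes it as "for subject who did not meet any of below criteria (refer to CSP section 3.1", so the list presents itself as a copy of the protocol criteria. Item 1.2b nevertheless reads "central laboratory HbA1c \geq 7.0 and \leq 10.5\% obtained at the screening visit (i.e.. Week -10".

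In the same row, the column for deviations relevant to the PP set covers randomised subjects with HbA1c "outside of specified limits such as more than 0.2% outside of specified limits", and explains this as "violation of inclusion criterion # 2c or screening HbA1c value out of range specified in 2a or 2b".

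On detection, SAP Section 2.2 says: "A report will be generated based on both IMPACT and programmatic checking results". That section also makes PP-relevant deviations a subset of important protocol deviations (IPDs), and says the list is finalised before unblinding.

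After early termination, SAP Section 4.4 keeps a listing of IPDs, a summary of the analysis sets and a listing of observed HbA1c. Section 6 drops every other planned analysis.

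**The concern.** Two current texts give different lower limits for one criterion, at one visit, in one stratum. The SAP text is the one that decides what counts as a deviation. A check programmed from it would accept a screening value that the protocol does not. Protocol Section 3 allows no exceptions to the eligibility criteria, so such a breach belongs on the IPD listing.

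The listing and the PP count are both among the few outputs that survive early termination. An error in the rule behind them can therefore still reach the study report.

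**Working it through.** **Step 1: compare all six limits.** Inputs are protocol Section 3.1, criteria 2a to 2c, and SAP Appendix 1, item 1.2.

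| Criterion | Limit | Protocol | SAP item 1.2 | Agree? |
|---|---|---|---|---|
| 2a, Stratum A screening | lower | 8.0% | 8.0% | yes |
| 2a | upper | 11.5% | 11.5% | yes |
| 2b, Stratum B screening | lower | 7.5% | 7.0% | **no** |
| 2b | upper | 10.5% | 10.5% | yes |
| 2c, Week -2, both strata | lower | 7.0% | 7.0% | yes |
| 2c | upper | 10.5% | 10.5% | yes |

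Five of six agree. The one that differs carries the Week -2 value, which item 1.2c repeats correctly in its own place. A copying slip from 2c to 2b is the simplest explanation, though the documents do not say so. As indirect support, the Stratum B enrolment-cap band in SAP Section 1.3 starts at 7.5%. Neither the SAP amendment history nor SAP Section 6 records a change to this limit.

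**Step 2: the band if the printed limit is used throughout.** A value is missed if it is below the protocol floor but not below the printed floor, so 7.0% ≤ HbA1c < 7.5%. The width is 7.5 − 7.0 = 0.5 percentage points. With values to one decimal (an assumption), these are 7.0, 7.1, 7.2, 7.3 and 7.4%. On this reading the PP floor also falls by 0.5: to 7.0% instead of 7.5% with no margin, or, with the 0.2 margin, to 7.0 − 0.2 = 6.8% instead of 7.5 − 0.2 = 7.3%.

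**Step 3: the band if the PP column means the protocol criteria.** The labels 2a, 2b and 2c in that column follow the protocol's numbering, so this reading is open. A randomised Stratum B subject is then PP-relevant below 7.3% (with the margin) or below 7.5% (without). A PP-relevant deviation is by definition an IPD and so belongs on the listing. What remains unlisted among randomised subjects is:

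- with the margin: 7.3% to below 7.5% (one-decimal values 7.3 and 7.4);
- without it: nothing.

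The full 0.5-point band and a protocol-based PP floor therefore cannot both hold for randomised subjects.

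**Step 4: what the error can reach.** Under SAP Section 4.4 it can reach the IPD listing and, if the printed limit is used for PP exclusion as well, the PP count. It cannot reach an efficacy estimate. The PP sensitivity analysis of HbA1c is dropped by Section 6, and the primary analysis was defined on the intent-to-treat (ITT) set.

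**The case against.** The strongest reply is that the list points to protocol Section 3.1, so a programmer following the pointer would code 7.5% and the printed 7.0% would do nothing. Nothing in the documents shows a check coded to 7.0%, and IMPACT is a second route to the same report. This stands: the omission is possible, not shown. It does not remove the mismatch, because the printed number and the pointer now give different instructions.

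A reader might infer that the whole band from 7.0% to below 7.5% will go unlisted while the PP floor stays at the protocol value. Step 3 shows why the documents do not support this for randomised subjects.

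A reader might also treat the loosely worded 0.2 margin as a further defect. Protocol Section 8.3.1 leaves the PP criteria to be set after deviation review, and both it and SAP Section 2.2 place the decision before unblinding, so the plan already provides for settling it.

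Finally, few subjects can be exposed. SAP Section 4.4 says no subjects were recruited in China. The planned non-China number was about 23 per arm, or 23 × 3 = 69. If the desired 33% Stratum B share applied there too, that is 69 × 0.33 ≈ 23 subjects. These are planned figures, not enrolment, but they indicate the scale.

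The retained listing of observed HbA1c is only partial protection. The documents do not say that it includes screening values, and it would not label them as deviations.

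**Conclusion.** The mismatch is certain: one of six HbA1c limits in item 1.2 differs from the criterion it restates, by 0.5 percentage points. The consequence is conditional. The unlisted Stratum B band is 7.0% to below 7.5% if the printed limit is used throughout. For randomised subjects it is at most 7.3% to below 7.5%, or empty, if the PP column applies the protocol criteria. Either outcome also assumes that IMPACT does not catch the subject.

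The documents give no actual enrolment, so the number affected is unknown and may be zero. A reader might infer that ineligible subjects were randomised, or that the efficacy results are at risk. The documents support neither: a wrong limit in a deviation list does not change who was admitted, and no retained estimate or test depends on it. Severity is minor.

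**What to change.** Reconcile SAP Appendix 1 item 1.2b with protocol criterion 2b (7.5% to 10.5%). Confirm that the programmatic deviation check uses the protocol limit, for both the IPD flag and PP exclusion. If unblinding has passed, document the correction and state whether any Stratum B subject had a screening value in the affected band.

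The cost is one number in the appendix and one confirmation of the check. Study conduct and the primary analysis are unchanged.

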### **Hematological/Oncological Diseases/Conditions**

- m. History of hemoglobinopathy, such as sickle cell anemia (SA), thalassemia or chronic or recurrent hemolysis, etc.
- n. Malignancy within 5 years of the screening visit (with the exception of treated basal cell or treated squamous cell carcinoma)

- o. Known immunocompromised status, including but not limited to, individuals who have undergone organ transplantation or who are positive for the human immunodeficiency virus (HIV)
- p. Donation of blood or blood products > 400mL or participation in a clinical study requiring withdrawal of > 400mL of blood within 6 months prior to the screening visit

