### **Sensitivity analysis**

To assess the robustness of the primary efficacy analysis for the change in HbA1c from baseline to Week 24, additional sensitivity analyses will be carried out using the following approaches:

1. A MMRM model, similar to the primary analysis, but including data after rescue and/or study treatment discontinuation, will be conducted.
2. Analysis of covariance (ANCOVA) model, with terms for treatment group, stratum, and baseline HbA1c value, including observations prior to rescue and study treatment discontinuation only, where LOCF data will be used for missing value at Week 24. The handling of LOCF is described in Section [3.1.6.1](#). The analysis will include data prior to the date of the first dose of rescue medication or up to 8 days post the last dose date of the double-blind study medication.

The following ANCOVA model will be used:

$$D_{24,ijk} = \text{Intercept} + \beta [Y_{0,ijk}] + \tau_i + s_k + \text{error}_{ijk}$$

where

- $D_{24,ijk} = Y_{24,ijk} - Y_{0,ijk}$  = the Week 24 or Week 24 LOCF change from baseline of subject  $j$  in treatment group  $i$  of stratification group  $k$ ,
- $Y_{0,ijk}$  is the baseline measurement of subject  $j$  in treatment group  $i$  of stratification group  $k$ ,
- $Y_{24,ijk}$  is the Week 24 or Week 24 LOCF measurement of subject  $j$  in treatment group  $i$  of stratification group  $k$ ,
- $\beta$  is the slope of  $D_{24,ijk}$  regressing on the baseline measurement and,
- $\tau_i$  is the mean effect of treatment group  $i$ .
- $s_k$  is the mean effect of randomisation stratification factor group  $k$ .
- $\text{Intercept}$ ,  $\beta$  and  $\tau_i$ ,  $s_k$  are unknown parameters to be estimated from the data.
- $\text{error}_{ijk}$  is the error term for subject  $j$  in treatment group  $i$  of stratification group  $k$ .

3. A MMRM model, similar to the primary analysis, using subjects in the Per Protocol Analysis Set who have a baseline assessment and any postbaseline assessment.

For each sensitivity analysis, the least squares mean estimates and 2-sided 95% confidence intervals for mean changes from baseline within and (when warranted) differences in mean change from baseline between each dapagliflozin treatment group and placebo will be provided.

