2.5	Did not fulfil eligibility criteria	
Hepatic Diseases
 
j. Significant hepatic diseases, including, but not limited to, chronic active hepatitis and/or severe hepatic insufficiency and/or significant abnormal liver function, including subjects with Alanine aminotransferase (ALT) and/or Aspartate aminotransferase (AST) > 3x Upper limit of normal (ULN) and/or Total Bilirubin (TB) > 2x ULN
 
k. Subjects with severe hepatic impairment (Child-Pugh class C)
 
l. Positive serologic evidence of current infectious liver disease, including subjects who are known to be positive for hepatitis A viral (HAV) IgM antibody, hepatitis B surface antigen (HBsAg), and hepatitis C virus (HCV) antibody
		
2.6	Did not fulfil eligibility criteria	
Hematological/Oncological Diseases/Conditions
 
m. History of hemoglobinopathy, such as sickle cell anemia (SA), thalassemia or chronic or recurrent hemolysis, etc.
 
n. Malignancy within 5 years of the screening visit (with the exception of treated basal cell
	3. Randomised subjects with a history of haemoglobinopathy with the exception of sickle cell trait (SA) or thalassemia; or chronic recurrent haemolysis. (i.e.	Completely Exclude from PP analysis set

IPD code	IPD Category	Explanation	PP Relevant IPD	Exclusion level
		
or treated squamous cell carcinoma)
 
o. Known immunocompromised status, including but not limited to, individuals who have undergone organ transplantation or who are positive for the human immunodeficiency virus (HIV)
 
p. Donation of blood or blood products > 400mL or participation in a clinical study requiring withdrawal of > 400mL of blood during within 6 months prior to the screening visit
	violation of exclusion criterion #2m)	

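### SAP Appendix 1 item 2.6 conflicts with protocol exclusion 2m, and with itself, on whether a randomised subject with thalassaemia leaves the per-protocol set

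*SAP*

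**What the plan says.** Protocol 3.2, under Hematological/Oncological Diseases/Conditions, excludes at 2m: "History of hemoglobinopathy, such as sickle cell anemia (SA), thalassemia or chronic or recurrent hemolysis, etc". No reason for the criterion is given.

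SAP 8.1 (Appendix 1) row 2.6 repeats that criterion in its Explanation column. Its PP-relevant column holds rule 3, which covers "Randomised subjects with a history of haemoglobinopathy with the exception of sickle cell trait (SA) or thalassemia" and, after a semicolon, chronic recurrent haemolysis. A bracketed pointer then equates the rule with "violation of exclusion criterion #2m". The consequence in the last column is complete exclusion from the PP set.

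SAP 2.2 says what such a rule is for: "IPDs that are determined to have the potential to affect the primary efficacy results are deemed PP Relevant IPDs". It also says what the rule does: "Subjects who have any PP relevant IPDs as detailed in appendix 1 will be excluded from the PP analysis set". The same section requires the list to be final before unblinding.

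The PP set feeds the third HbA1c sensitivity analysis in SAP 4.2.4.2: "A MMRM model, similar to the primary analysis, using subjects in the Per Protocol Analysis Set". SAP 4.2.2 also repeats the baseline summaries on it.

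**The concern.** A rule that claims to apply a criterion should not exempt by name a condition which that criterion excludes by name. Here the two statements sit in adjoining columns of one table row. A subject with a history of thalassaemia, randomised in error, is an important deviation under 2m. Whether that subject is in the PP set depends on which half of rule 3 the programmer follows.

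The abbreviation adds a second ambiguity. In 2m and in the protocol's abbreviation list, SA is sickle cell anaemia. Rule 3 puts SA after sickle cell trait, a condition that 2m does not mention. A reader who goes by the abbreviation could exempt sickle cell anaemia as well.

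The PP analysis is a robustness check on the primary variable, HbA1c. Row 2.6 covers four criteria, 2m to 2p, and only 2m carries a PP-relevant rule. The SAP therefore treats haemoglobinopathy as a deviation that could affect the primary result, and then lets out one of its named forms without giving a reason.

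**Working it through.** The plan states no figure on this point, so the check is a comparison of texts followed by a trace of where the PP set is used.

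**Step 1. The texts side by side.**

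| Condition | Protocol 2m and SAP 2.6 Explanation | Rule 3, exception taken literally | Rule 3, pointer to 2m taken literally |
|---|---|---|---|
| Thalassaemia | Excluded by name | Stays in PP | Leaves PP |
| Sickle cell anaemia | Excluded by name | Unclear: the word trait says it leaves, the label SA says it stays | Leaves PP |
| Sickle cell trait | Not named; the list in 2m is open-ended | Stays in PP | Depends on whether 2m covers it |
| Chronic or recurrent haemolysis | Excluded by name | Leaves PP if both chronic and recurrent, because the word 'or' has been dropped | Leaves PP |

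The semicolon in rule 3 closes the exception before haemolysis, so haemolysis is a further ground for removal and not part of the exemption. The first row is the contradiction: a subject cannot be both exempt from the rule and an instance of the violation that the rule says it is.

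**Step 2. Who can be affected.** Protocol 3.4 forbids randomising ineligible subjects, so only those randomised in error are concerned. Criterion 2m rests on history. Neither the schedule in protocol Table 1 nor the laboratory list in Table 3 includes a dedicated haemoglobinopathy test, so a history can come to light after randomisation.

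**Step 3. Where the PP set is used.**

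| Output | Analysis set | Touched by rule 3? |
|---|---|---|
| Primary HbA1c model (protocol 8.5.1, SAP 4.2.4.2) | ITT | No |
| HbA1c sensitivity analysis 3 (SAP 4.2.4.2) | PP | Yes, as planned |
| HbA1c response below 7.0% (SAP 4.2.4.3) | ITT by the default in SAP 4.2.4 | No |
| HbA1c eligibility, 7.0% to 10.5% at Week -2 | Decided before any PP classification | No |
| Baseline summaries (SAP 4.2.2) | Repeated on PP | Yes |

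**Step 4. Effect of early termination.** SAP 6 drops every planned analysis except those in 4.4. Section 4.4 keeps a summary of the analysis sets, which include the PP set, and the baseline tables of 4.2.2. It lists important deviations and observed HbA1c but specifies no PP model. What remains exposed is the PP count and any PP baseline table. A subject with thalassaemia would appear in the deviation listing whichever way rule 3 is read.

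**Step 5. Size.** The documents give neither a frequency of thalassaemia nor a rate of randomisation in error. Purely as an assumption, take 1% to 3% of randomised subjects with a thalassaemia history found late:

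- On the planned 342: 342 × 0.01 = 3.4 and 342 × 0.03 = 10.3.
- On the planned enrolment outside China, about 23 per arm, 3 × 23 = 69: 69 × 0.01 = 0.7 and 69 × 0.03 = 2.1.

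SAP 4.4 states that the study closes without recruiting in China, so the second base is the closer one. It is still a planned number, not an observed one.

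**The case against.** The strongest reply is that PP rules are allowed to be narrower than the eligibility criteria. Protocol 8.3.1 removes only deviations that could affect interpretation of primary efficacy, and leaves the criteria to be settled after deviation review. SAP 2.2 treats PP-relevant deviations as a subset, and most eligibility rows in Appendix 1 have no PP consequence. This stands. A reader might infer that the SAP breaches the protocol merely by keeping some 2m violators in the PP set; the documents do not support that.

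Second, PP-relevant rule 1 uses the same device: it allows a margin of 0.2% on the HbA1c limits and then points to the inclusion criterion as violated. So a pointer to a criterion does not prove that rule and criterion are meant to be identical. This stands in part. A margin on a numerical limit is a tolerance, whereas rule 3 exempts by name what 2m excludes by name. Rule 4, on free T4, uses the same pointer with no exemption. SAP 6 records no intended change and no rationale appears anywhere.

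Third, the word trait may govern both nouns, which would exempt carriers only. The text does not settle this, and it is a further reason to rewrite the cell.

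Two stronger readings are tempting. A reader might infer that the protocol regards HbA1c as unreliable in thalassaemia. The protocol gives no reason for 2m, and the nearest support is the general definition of PP relevance in SAP 2.2. A reader might also carry the concern over to the 7.0% to 10.5% randomisation range or to the responder endpoint, but neither uses the PP set.

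**Conclusion.** The inconsistency is real and of low severity. Row 2.6 contradicts protocol 2m and itself, so PP membership of a subject with thalassaemia randomised in error is undetermined: in by the exception, out by the pointer. The label SA is misapplied.

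As planned, the consequence is confined to HbA1c sensitivity analysis 3 and the PP baseline tables. Under the current SAP it is confined to the PP count and any PP baseline summary. The primary conclusion is not at risk.

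The number of subjects cannot be computed from the documents. The range of 3 to 10 that a reader might take from the planned 342 rests on assumed rates and on a base that includes China. With the same assumed rates and the planned enrolment outside China, it is about 1 to 2. The true number is probably very small and may be zero.

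The conclusion that such a subject stays in assumes that the semicolon closes the exception and that trait qualifies only sickle cell. The conclusion that the row needs reconciling depends on neither assumption.

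**What to change.** Before unblinding, reconcile rule 3 with 2m by deleting the exception. Suggested content: a randomised subject with a history of any haemoglobinopathy, sickle cell anaemia and thalassaemia included, or of chronic or recurrent haemolysis, violates 2m and is completely excluded from the PP set. This also restores the 'or' between chronic and recurrent.

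If a narrower exemption is intended, for example carriers only, then define the exempt conditions explicitly, remove the statement that the rule equals a violation of 2m, give the reason, and use SA only for sickle cell anaemia.

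The cost is one appendix cell and one line in the SAP amendment history. The PP set may lose a few subjects at most, and no other analysis set changes.
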